From the earlier conservative mortality assumptions, we expect 240 (11%) or more all-cause mortality events among the 2100 COPD patients during the course of SPIROMICS. For tests of direct association of potential surrogate endpoints/markers with this outcome, we consider for simplicity a dichotomized surrogate endpoint with relative frequency 0.50 for each value of the surrogate. In order for surrogate endpoint to demonstrate promising utility for further prospective validation in the context of a clinical trial, we propose that the surrogate confer an odds ratio of 1.8 or more. The correlation structure of the potential surrogates is not known a priori, so we use a significance level of 0.001 in order to account for multiplicity of testing (corresponding to a Bonferroni correction for 50 tests). Under these assumptions and assuming retention of 92%, a contingency table test of mortality vs. the surrogate will have 77% power to reject the null hypothesis.

7.2. *Interim Study Progress Reports*

7.2.1. *Steering Committee Reports*

Monthly management reports are prepared by the GIC and provided to the Steering Committee for monitoring of study progress. Tables and figures summarizing enrollment, completion of study procedures and visits, and baseline characteristics are included.

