The second approach to subgroup finding posits that individualized therapies based upon a patient’s genotype are possible. DNA collection followed by either genome-wide association or specific genetic tests combined with statistical analyses will allow us to evaluate this hypothesis and to continue to unravel the correlation between underlying genetics and resultant phenotypes. Several genes have been recently reported to be associated with COPD phenotypes (see, e.g., Wood, Tan, and Stocklye, 2009 *Genome Medicine* 1:112). Concurrently run studies (e.g., the COPDGene Study (COPDGene Investigators, 2010)) will add to this list, and SPIROMICS will

be valuable in validating newly emergent findings from these studies. An example of a specific hypothesis under this approach is:

- SPIROMICS participants with SNPs previously associated with FEV₁ decline (CHRNA3/5, EPHX1, GSTP1, and HHIP) will have faster rates of decline in FEV₁ over three years than participants without those SNPs.

The third approach to subgroup finding suggests that components of COPD syndrome can be prospectively identified that are associated with a worse prognosis, as measured by morbidity over a 3-year period, when compared to participants without those components. There are many specific examples of this general hypothesis, including the following:

- Participants with apical emphysema at baseline will have more exacerbations resulting in a hospitalization over three years than those without apical emphysema.

Hypothesis #2 – Intermediate Outcome Identification: This general hypothesis can more specifically be stated as: SPIROMICS will identify intermediate outcome measures that predict long-term clinical endpoints of morbidity. Such outcomes may be markers of short-term change (1 year) that predict long-term change (3 years), or they may be markers that change with exacerbations and are predictive of more severe long-term morbidity/mortality.

For example:

- The novel molecular methodologies employed in SPIROMICS (including T-RFLP, phylochips, and deep-sequencing) will provide candidate markers that correlate with more frequent exacerbations and are therefore predictive of long-term morbidity/mortality.

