The identification and validation process consists of a two-part screening step in which each of a pool of intermediate outcomes is examined for (a) correlation with respect to the four study design strata defined above and (b) correlation with the clinical endpoints assessed after three years of follow-up. For step (a), the term “correlation” will refer to any association between the intermediate outcome and the design strata, with no order restrictions. For step (b), it is generally understood that the most useful relationships between surrogates and clinical endpoints are monotone, therefore test statistics that are powerful for evaluation of monotone relationships are favored. Intermediate outcomes are handled as univariate measures, such as change from baseline to Year 1 values of a continuous measurement or presence/absence of a biological or clinical marker assessed at Year 1. Each intermediate outcome will be regressed on baseline covariates thought *a priori* to be important predictors, including, gender, height, weight, and clinical site. Linear models will be used for both continuous and dichotomous outcomes to produce residuals, which form the basis for the correlation tests. Least squares estimation will be employed at this step, because the focus is on examining correlations between the residuals and disease severity, after adjusting for baseline covariates, and not on prediction. The model residuals for the pool of intermediate outcomes will then be analyzed for significant trends with respect to design stratum using permutation to control the family-wise error rates for the number of potential surrogates (Westfall and Young, 1993). This approach will keep the entire set of residuals intact, permuting with respect to the clinical endpoints, and benefit from any positive correlation among intermediate outcomes in order to avoid overly stringent significance thresholds.

Candidate markers will also be identified based on previous studies or findings in the literature and considered for evaluation in SPIROMICS. Methods such as examining signal-to-noise ratios will be employed for this evaluation. For example, decline in lung density measured by computed tomography (CT) has been shown to track disease progression in emphysema patients (Stolk, et al., 2007). The signal-to-noise ratio for lung densitometry was found to be 2.5-fold that of decline in lung function or gas diffusion based on 144 COPD patients followed over 30 months.

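### Binary markers may be screened as Year 1 status alone, with no named adjustment for their own baseline status, so the screen cannot separate a static prognostic trait from an informative one-year change

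*Protocol*

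**What the plan says.** Section 7.4.3 treats each intermediate outcome as a univariate measure and gives two example forms. A continuous marker enters as "change from baseline to Year 1 values of a continuous measurement". A binary marker enters as "presence/absence of a biological or clinical marker assessed at Year 1", with no reference to its earlier value.

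Each outcome is regressed on "baseline covariates thought *a priori* to be important predictors, including, gender, height, weight, and clinical site". The residuals then go through a two-part screen: "a) correlation with respect to the four study design strata defined above and (b) correlation with the clinical endpoints assessed after three years of follow-up". Step (a) accepts any association with the strata. Step (b) favours tests for monotone relationships. Permutation controls the family-wise error rate. A further stage, condition (2) of the Prentice criteria, uses differences among severity categories and controls in place of treatment differences.

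The target is stated in sections 3.1.2 and 7.3: "Such outcomes may be markers of short-term change (1 year) that predict long-term change (3 years"), or markers that change with exacerbations and predict worse long-term outcome. Section 3.1.2 gives following parameters over time as the reason for measuring them at baseline, one year and three years.

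Section 7.1 powers a test of mortality against a dichotomized surrogate and concludes that "a contingency table test of mortality vs. the surrogate will have 77% power to reject the null hypothesis".

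**The concern.** The two example forms answer different questions. Change from baseline removes whatever was already fixed at entry. Year 1 presence or absence keeps all of it. A binary marker that never changes in any patient has the same value at Year 1 as at baseline, so it carries only baseline prognostic information, yet it is eligible for the screen on the same footing as a marker whose one-year change matters.

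No later stage is built to separate the two. Step (a) asks whether the marker differs between strata, and a fixed trait that is commoner in severe disease does. Condition (2), as adapted here, also compares groups of patients. Permutation controls false positives, but a prognostic trait is truly associated with outcome and is not a false positive. All three look at differences between patients and none at change within a patient.

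At stake is the meaning of the Aim 2 product. A list of candidate intermediate outcomes would mix binary markers whose one-year change is informative with markers for which the study shows only baseline prognosis, and a reader could not tell which is which.

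**Working it through.** **Reproducing the 77%.** Inputs from section 7.1: "we expect 240 (11%) or more all-cause mortality events among the 2100 COPD patients"; marker prevalence 0.50; odds ratio 1.8; alpha 0.001, two-sided; retention 92%.

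- N = 2,100 × 0.92 = 1,932, so 966 per marker group.
- Overall risk = 240/2,100 = 0.1143.
- Solve 0.5·p0 + 0.5·p1 = 0.1143 with p1 = 1.8·p0/(1 − p0 + 1.8·p0). This gives p0 = 0.0851 and p1 = 0.1435.
- Null SE = √(2 × 0.1143 × 0.8857/966) = 0.01448. Critical difference = 3.2905 × 0.01448 = 0.0476.
- Alternative SE = √((0.0851 × 0.9149 + 0.1435 × 0.8565)/966) = 0.01442.
- Power = Φ((0.0583 − 0.0476)/0.01442) = Φ(0.742) = 77.1%.

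The stated figure reproduces. Nothing in it depends on the marker having changed.

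**Status that is stable but only prognostic at baseline.** Assume that death depends on baseline status alone, with the risks above, and that a proportion r of patients have the same status at Year 1, the remainder switching at random. By Year 1 status the risks are r·p1 + (1 − r)·p0 and r·p0 + (1 − r)·p1, so their difference is (2r − 1) × 0.0583. The same power formula gives:

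| Persistence r | Risk difference by Year 1 status | Probability significant, Year 1 status alone | Same, given baseline status |
|---|---|---|---|
| 100% | 0.0583 | 77.1% | 0% (no variation left) |
| 95% | 0.0525 | 63.2% | about 0.1% |
| 90% | 0.0467 | 47.3% | about 0.1% or less |
| 80% | 0.0350 | 19.1% | about 0.1% |

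The last column comes from simulation (two separate sets, of 1,500 and 4,000 runs per level). It is the nominal 0.1% error rate, as it must be when Year 1 status adds nothing. For the status-alone column the simulations gave about 77%, 62 to 66%, 46 to 48% and 18 to 20%, in line with the closed form.

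**Sensitivity to the inputs.** With full persistence and 50% prevalence, the 77% becomes 7% at odds ratio 1.3, 31% at 1.5 and 92% at 2.0. At odds ratio 1.8 and 10% prevalence it is 38%.

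**Timing of deaths.** A marker assessed at Year 1 cannot be related to deaths before Year 1, but section 7.1 counts all 240. The protocol does not give the share in the first year. If it is 20%, 33% or 40% (assumed), the power falls to about 64%, 52% or 46%.

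**Difference score or conditioning.** In the 4,000-run simulation an unadjusted difference (Year 1 minus baseline) was significant in 0.9%, 2.0% and 6.5% of runs at 95%, 90% and 80% persistence, because it is correlated with baseline status. Conditioning on baseline status holds the 0.1% level.

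**The case against.** Several stronger readings are tempting, and the document does not support them.

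- *All Year 1 markers are screened without their baseline.* Not so. Continuous measures are given as change from baseline, and the spirometry and CT measures listed in sections 6.4.1.6 and 6.4.4.4 fit that form. The point is confined to binary markers.
- *Baseline status is excluded.* It is unnamed. The covariate list is open, the outcome forms are examples, and section 7.3 leaves detailed plans to each hypothesis. This weakens the point but does not remove it: section 7.3 also says that the methods are described in detail in these subsections, and 7.4.3 positively offers a status-only form.
- *A static trait passes the whole screen 77% of the time.* The 77% is one mortality test at one odds ratio and prevalence. Section 7.1 does not say when the surrogate is measured. Step (a), the permutation control and condition (2) were not modelled.
- *Genotypes will be put forward as surrogates.* They are handled separately, under subgroup finding (7.3) and association mapping (7.4.2).
- *A marker that stays stable cannot show a treatment effect, so trials built on it would fail.* This does not follow. The study tests no therapy, and a marker that persists in this cohort might still respond to a drug. Section 7.4.3 values association of the surrogate or of its changes, and section 3.1.2 calls the results candidates for validation. Excluding stable markers would be unjustified.

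The objection that survives in full is the last: it rules out a hard exclusion rule. It does not answer the complaint that the analysis leaves two kinds of evidence undistinguished.

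**Conclusion.** The point holds for binary markers. Section 7.4.3 admits Year 1 status with no named adjustment for baseline status, while the stated target is change, and no later stage tests within-patient change. In the illustrative mortality test, a marker with only baseline prognostic value is significant with probability about 77%, 63%, 47% and 19% at 100%, 95%, 90% and 80% persistence, against about 0.1% or less given baseline status.

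This rests on the section 7.1 inputs, on counting all deaths from baseline, and on the assumption that only baseline status is prognostic, which makes the adjusted comparison null by construction. The persistence levels are assumed. The figures show that the test cannot discriminate; they do not predict how many such markers will be found. This is a weakness of analysis and labelling in a co-primary aim, correctable without new data.

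**What to change.** In section 7.4.3, for binary markers measured at both baseline and Year 1, add the marker's own baseline status to the step (b) analysis, so that the test is of Year 1 status given baseline status. Report each such marker with and without this adjustment. Describe a marker associated only without it as prognostic at baseline, with no evidence here that its one-year change is informative, and keep it on the candidate list under that description. Use conditioning in preference to a simple difference score, for the reason shown in the working. State also that the 77% in section 7.1 does not distinguish a static prognostic trait from a changing marker.

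The cost is wording and one more term in an existing regression. Table 3 already schedules blood, urine, CT, spirometry and questionnaires at both visits. There are two drawbacks. The adjusted analysis has less power for slowly changing markers, which is why both results should be shown. Induced sputum is repeated after baseline only where the baseline collection failed, so most sputum markers will lack the pair of values and cannot be analysed this way.

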7.4.3. Intermediate Outcome Identification and Initial Validation

Validating biomarkers or surrogate endpoints is quite challenging, especially if the goal is to satisfy the Prentice criteria for surrogate validity (Prentice, 1989). The Prentice criteria demand two conditions of a surrogate S for a primary endpoint T : (1) that S and T be correlated (i.e., not independent) and (2) that a test of the null hypothesis of no treatment effect on S is equivalent to a test of the null hypothesis of no treatment effect on T . In applying the Prentice criteria,

candidate surrogates are first screened relative to condition (1) by examining the correlation between the candidate surrogates and clinical endpoints of interest. The primary clinical endpoints in SPIROMICS are all-cause mortality, exacerbations, and decline in FEV₁, over three years. In addition, baseline measures such as initial FEV₁ will be used as secondary measures for surrogate candidate discovery. At the second stage, a test of condition (2) is carried out. With novel surrogate candidates, such as those anticipated for SPIROMICS, sets of completed clinical trials are likely not available. The approach planned here is to view differences among disease severity categories and controls as analogues of treatment group differences, and proceed with screening candidate surrogates using the methods of Daniels and Hughes (1987) for condition (2). The design of SPIROMICS is observational, involving no randomized conditions. Thus any findings of association between clinical endpoints and candidate surrogates will not establish causality of disease severity on the biomarker (or vice versa). However, association of a potential surrogate (or changes in the surrogate) with clinical endpoints occurring prospectively in the study will offer powerful evidence of the potential utility of the surrogate for future trial design.

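### The surrogate screen adjusts only the marker for covariates; where those covariates also predict stratum or endpoint, correlations shrink and the permutation test is miscalibrated, usually losing power

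*Protocol*

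**What the plan says.** Section 7.4.3 describes a two-part screen of candidate intermediate outcomes: (a) association with the four design strata and (b) correlation with the three-year clinical endpoints. On the endpoints it says: "The primary clinical endpoints in SPIROMICS are all-cause mortality, exacerbations, and decline in FEV₁, over three years".

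Each intermediate outcome is first regressed on baseline covariates thought "to be important predictors, including, gender, height, weight, and clinical site". The next step is fixed: "Linear models will be used for both continuous and dichotomous outcomes to produce residuals, which form the basis for the correlation tests". Least squares is justified because "the focus is on examining correlations between the residuals and disease severity, after adjusting for baseline covariates, and not on prediction".

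The marker residuals are then analysed against design stratum "using permutation to control the family-wise error rates for the number of potential surrogates". The mechanics are: "This approach will keep the entire set of residuals intact, permuting with respect to the clinical endpoints".

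Nothing in the section regresses the stratum or the clinical endpoint on the same covariates. For the stratum, one-sided adjustment is explicit. For the endpoints, it follows from what is permuted and from the absence of any adjustment step.

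The only power figure for a test of a surrogate is in section 7.1: "a contingency table test of mortality vs. the surrogate will have 77% power to reject the null hypothesis". It assumes an odds ratio of 1.8, a 50/50 marker, significance level 0.001 and 92% retention.

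**The concern.** The stated aim is association after covariate adjustment. Correlating a residualised marker with a raw endpoint gives the semipartial correlation, which is smaller than the partial correlation whenever the covariates explain part of the endpoint. Permuting the raw endpoint also mixes that explained variation into the reference distribution, so the critical value is set for a noisier endpoint than the one the marker is really tested against.

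Section 7.4.3 wants the permutation step to avoid thresholds that are too strict, and this feature works against that wish. The screen is the route to Primary Aim 2 (section 3.1.2), so a real marker that just misses the family-wise threshold is dropped from the candidate list for a reason unrelated to its merit.

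**Working it through.** **1. The plan's own figure.** Inputs from section 7.1: 240 deaths in 2,100 COPD patients (11.43%), odds ratio 1.8, 50/50 marker, two-sided alpha 0.05/50 = 0.001, 92% retention. That gives 0.92 × 2,100 = 1,932 patients, or 966 per marker group. The two risks with odds ratio 1.8 and mean 0.1143 are 0.0851 and 0.1435, a difference of 0.0583.

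- Null SE: sqrt(2 × 0.1143 × 0.8857 / 966) = 0.01448.
- Alternative SE: sqrt((0.0851 × 0.9149 + 0.1435 × 0.8565) / 966) = 0.01442.
- Power: Φ((0.0583 − 3.2905 × 0.01448) / 0.01442) = 77.1%.

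The stated 77% is reproduced. It is for an unadjusted test and serves here only as a benchmark.

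**2. The algebra.** Let e be the marker residual, y the centred endpoint and u the endpoint residual on the same covariates. Least squares makes e orthogonal to the fitted part of y, so e'y = e'u. Hence

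r(e, y) = e'u / (|e||y|) = r(e, u) × |u|/|y| = partial r × sqrt(1 − R2).

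Permuting y gives a null SD of about 1/sqrt(n). With equal variances the true null SD is sqrt(1 − R2)/sqrt(n). A nominal critical value z therefore acts as z/sqrt(1 − R2), and the true size is 2 × (1 − Φ(z/sqrt(1 − R2))).

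**3. Size and power by assumed R2.** The protocol gives no R2; the values below are assumptions. The benchmark marker has 77.1% power when both sides are adjusted. Power with the raw endpoint is shown under two approximations: (A) critical value divided by sqrt(1 − R2), and (B) standardised effect multiplied by sqrt(1 − R2).

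| R2 | sqrt(1 − R2) | Power A | Power B | Size at 0.05 | Size at 0.001 |
|---|---|---|---|---|---|
| 0 | 1.000 | 77.1% | 77.1% | 0.050 | 0.00100 |
| 0.02 | 0.990 | 76.1% | 75.8% | 0.048 | 0.00089 |
| 0.05 | 0.975 | 74.4% | 73.9% | 0.044 | 0.00074 |
| 0.10 | 0.949 | 71.3% | 70.3% | 0.039 | 0.00052 |
| 0.20 | 0.894 | 63.7% | 62.3% | 0.028 | 0.00023 |
| 0.30 | 0.837 | 53.8% | 53.2% | 0.019 | 0.00008 |

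Example, R2 = 0.10 under A: 3.2905 × 0.01448 / 0.949 = 0.0502, and Φ((0.0583 − 0.0502) / 0.01442) = 71.3%. The losses are 2.7 to 3.2, 5.8 to 6.8 and 13.4 to 14.8 points at R2 = 0.05, 0.10 and 0.20.

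**4. Simulation of the planned test.** A maximum-|r| permutation test was run over 50 correlated markers against the four strata at 92% retention (250 runs; Monte Carlo SE about 0.014 for family-wise error, about 0.03 for power).

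| R2 | Semipartial/partial ratio | Family-wise error, raw / both adjusted | Power for one true marker, raw / both adjusted |
|---|---|---|---|
| 0 | 1.000 | 0.060 / 0.056 | 0.58 / 0.58 |
| 0.05 | 0.975 | 0.048 / 0.064 | 0.58 / 0.63 |
| 0.20 | 0.894 | 0.016 / 0.036 | 0.46 / 0.58 |
| 0.40 | 0.775 | 0.000 / 0.068 | 0.26 / 0.62 |

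**5. Unequal variances.** Section 7.4.3 covers dichotomous markers, and exacerbations are an endpoint. Assumed setting: marker prevalence 5% versus 30% across a binary covariate, overdispersed counts with mean 2 or 3 versus 4.5, and marker and count independent given the covariate (1,000 runs; SE about 0.8 points). At nominal 5% the raw-endpoint test rejected 7.0% to 7.2%. With the prevalences reversed and means 2 versus 4.5, it rejected 1.1%. Residualising both sides did not cure this (7.8% to 8.3%, and 1.7%). A studentised statistic on two-sided residuals, in a large-sample version of the test, gave about 5% in the anti-conservative settings.

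**The case against.** The strongest reply is that the size of the effect is unknown and may be small. Strata are defined by FEV1/FVC, a lower limit of normal and FEV1 percent predicted (section 5.3.1), and centres recruit equal numbers of men and women. There is little reason to expect gender or height to explain much of the stratum. At R2 of 5% or less, the loss is about 3 points or fewer. This stands, and it is why the figures are conditional. Links are still plausible: sections 4.1.3.1 and 6.4.2.1 treat body mass index as a mortality predictor, and section 7.4.3 uses initial FEV1 as a secondary measure, which would depend on sex and height if analysed in litres.

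It can also be said that section 7.3 promises a detailed plan for each hypothesis, that no test statistic is named for step (b), and that this is an initial screen with no causal claim. That limits the consequence, but the residualising and permutation steps are stated method, not details left open.

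A reader might infer several stronger things that the protocol does not support:

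- That every correlation is attenuated. This needs R2 above zero.
- That the test is always conservative. The unequal-variance case shows otherwise.
- That all effect sizes are understated. By the Frisch-Waugh-Lovell result, the slope of the raw endpoint on the residualised marker equals the slope from the joint model. The shrinkage applies to standardised correlations and to marker residuals compared across raw strata.
- That exacerbation rates vary by site. Section 6.7.2.3 says only that the location of care may differ regionally, and for that reason pools emergency and office visits.
- That the 77% in section 7.1 is wrong. It reproduces for the test it describes.

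**Conclusion.** The concern holds in conditional form. The screen adjusts one side only, so it is miscalibrated wherever gender, height, weight or site also predict the stratum or endpoint. With roughly equal variances the direction is conservative. At R2 between 5% and 20%, power falls from a 77% benchmark to between about 74% and 62%, and true size at nominal 0.001 falls to between 0.00074 and 0.00023. With dichotomous markers and overdispersed counts the error can go either way.

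These figures rest on assumed R2 values, on a benchmark borrowed from the unadjusted mortality test, and on assumed prevalences and count means for the unequal-variance case. The one-sided reading is certain for the stratum and inferred for the endpoints. The change is worth making because it is cheap and costs essentially nothing if R2 is near zero; the protocol does not show that the loss is large.

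**What to change.** In section 7.4.3, state that the stratum indicators or clinical endpoint are residualised on the same covariates as the marker before the test. Alternatively, fit endpoint on marker plus covariates and permute residuals within that model, for example by the Freedman-Lane scheme. Use a studentised, heteroscedasticity-robust statistic, since two-sided residualising alone does not correct for unequal variances. Keep the Westfall-Young maximum-statistic step, with each permutation applied jointly to all markers so that their correlation is preserved.

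It would also help to report the observed R2 of each endpoint and of the strata on the covariates, so that the reader can see how much the adjustment mattered.

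The cost is a sentence or two in the plan and slightly more analysis work. No new data are needed, and the sample size and the section 7.1 power statement can stay as they are.
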